10.1.2 End of Study Definition

The end of study is defined as the date of the last scheduled study procedure as outlined in the Study Events Flow Chart ([Section 6](#)).

11 STUDY POPULATION

11.1 Inclusion Criteria

Patients must fulfill all of the following inclusion criteria to be eligible for participation in the study:

1. ESRD maintained on stable outpatient HD regimen, using an established (> 3 months) and normally functioning, regular flow, uninfected first mature AV fistula (or AV graft) and skin consistent with standard chronic HD access injuries, and HD stability defined as $Kt/V \geq 1.2$ within 3 months prior to screening at a healthcare center for > 3 months from screening.
2. On HD regimen at least 3 times per week for a minimum of 3 hours per dialysis session, using a complication-free well maintained AV fistula (or AV graft), expected and plan to continue this throughout and for at least 3 months beyond the study.
3. Is capable of understanding the written informed consent, provides signed and witnessed written informed consent, and agrees to comply with protocol requirements and study-related procedures.
4. Willing to be confined to the CRU for the duration of the study, able to comply with all study-related requirements, and able to adhere to study restrictions and visit schedules.
5. Male or female, between 18 and 80 years of age (inclusive) at the time of screening.
6. BMI of ≥ 18 at the time of screening.
7. Considered by the PI to be clinically stable with respect to underlying ESRD, based on medical evaluation that includes medical and surgical history, and a complete physical examination including vital signs, ECG, and clinical laboratory test results at screening. Repeat assessments are permitted for any laboratory, ECG, or vital sign parameter required for enrollment.
8. Female patients must be of non-childbearing potential and must have undergone one of the following:
 - sterilization procedures at least 6 months prior to dosing;
 - hysteroscopic sterilization;
 - bilateral tubal ligation or bilateral salpingectomy;
 - hysterectomy;
 - bilateral oophorectomy;or be postmenopausal with amenorrhea for at least 1 year prior to dosing and follicle-stimulating hormone (FSH) serum levels consistent with postmenopausal status as per PI or designee judgment.

9. Male patients must either be sterile (vasectomy with history of a negative sperm count following the procedure); practice total abstinence from sexual intercourse as the preferred lifestyle (periodic abstinence is not acceptable); use a male condom with any sexual activity; or agree to use a birth control method considered to be appropriate by the Investigator (such as one of the methods identified above for female patients) from the time of screening until 90 days after study drug administration. Male patients must agree not to donate sperm for a period of 90 days after study drug administration.

11.2 Exclusion Criteria

Patients must not be enrolled in the study if they meet any of the following criteria:

1. Documented history of acute vasoocclusive thrombotic event (acute coronary syndrome, stroke or transient ischemic attack, venous thromboembolic event), or vascular access fistula or AV graft failure in the past 3 months.
2. With the exception of unfractionated heparin during HD, concomitant or prior use of anticoagulant/antiplatelet agents (e.g., low molecular weight heparins, warfarin, apixaban, bivalirudin, ticagrelor, edoxaban, dabigatran, rivaroxaban, clopidogrel, prasugrel, ticlopidine, eptifibatide, tirofiban, dipyridamole, diclofenac, and all other NSAIDs) that may affect hemostasis for 2 weeks prior to check-in on Day -8 and throughout the study.
3. Use of unfractionated heparin for HD sessions from check-in on Day -8 and throughout the study.
4. Any clinically significant (CS) concomitant disease or condition (including treatment for such conditions) that, in the opinion of the PI, could either interfere with the study drug, compromise interpretation of study data, or pose an unacceptable risk to the patient.
5. Any other CS abnormalities in laboratory test results at screening that would, in the opinion of the PI, increase the patient's risk of participation, jeopardize complete participation in the study, or compromise interpretation of study data.
6. Pregnant (positive pregnancy test) at screening or check-in on Day -8. If serum human chorionic gonadotropin (hCG) pregnancy test results are indeterminate, follow-up testing should be performed to determine eligibility.

All female patients will not be pregnant and will have a negative pregnancy test at screening and check-in on Day -8, with the following exception: females receiving dialysis with an indeterminate pregnancy test result or persistently low hCG resulting in a false positive pregnancy test may be included in the study at the discretion of the PI. Postmenopausal patients with a result outside the postmenopausal range or an indeterminate pregnancy test will undergo additional testing with FSH to confirm postmenopausal status prior to study enrollment.

7. Treatment with another investigational drug or device study within 30 days (or 5 half-lives, whichever is longer) prior to check-in on Day -8.

8. Acute illness that is considered by the PI to be CS within 2 weeks of check-in on Day -8.
9. Currently have established underlying inherited or acquired symptomatic bleeding disorders and/or are at risk for excessive bleeding per PI judgment or current active bleeding (e.g., gastrointestinal, intracranial), aside from minor bleeding from the puncture site on the AV fistula or AV graft, which would be expected to occur during the dialysis procedure, with the following values:
 - Platelet count < 100,000 cells/mm³ (if < 100,000 but > 75,000 cells/mm³, with permission of PI and medical monitor) at screening
 - INR > 1.4 at screening
 - aPTT up to 1.2 x ULN (if >1.2x ULN up to < 1.5 x ULN, with permission of PI and medical monitor) at screening
 - ALT or AST > 2 x ULN at screening
 - Total bilirubin > 1.2 ULN at screening
 - Hemoglobin concentration < 10 g/dL at screening
10. Seated blood pressure < 90/40 mmHg at screening and check-in on Day -8.
11. Exclusion criteria for ECG at screening and check-in on Day -8:

| | |
|--|--------------------|
| Heart rate | < 45 and > 110 bpm |
| QTcF interval | > 500 msec |
| bpm = beats per minute; msec = milliseconds; QTcF = QT interval corrected using Fridericia's formula | |
12. History of a CS allergy to recombinant biologic drug, rodents, or a known sensitivity or idiosyncratic reaction to any compound present in xisomab 3G3, its related compounds, or any compound listed as being present in the study formulation.
13. Participate in strenuous exercise from 48 hours prior to check-in on Day -8 and throughout the study.
14. Positive test for drugs of abuse and/or positive alcohol test at screening or check-in on Day -8 if not accounted for by a prescription medication. Patients with a positive test based on a prescribed medication may be enrolled.

15. Positive test at screening for hepatitis B surface antigen (HBsAg) or human immunodeficiency virus (HIV). If a patient with ESRD has positive test results for hepatitis C virus (HCV) but liver function tests are otherwise not clinically significant, the patient may be included at the PI's discretion.
16. Receiving blood purification therapy other than HD.
17. Any other reason that would render the patient unsuitable for study enrollment at the discretion of the PI.

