1 PROTOCOL REVISION HISTORY

| Date/Name | Description |
|-----------------------------------|---|
| 14June2018 by [name] | 
Final Protocol, Amendment 1
 
Following review by the Institutional Review Board, this protocol is being amended to provide justification for the use of a placebo-control design. In addition, information on safety measures that will be undertaken by the Investigators should there be clotting in the extracorporeal circuit has been added.
 
Thus, Section 8.4.1 Rationale for this Study and Study Design, Section 8.5 Risks and/or Benefits to Patients, and Section 11.3 Early Termination of Patients from the Study were updated. Section 13.3 Hemodialysis Procedure and Blood Clots in the Dialyzer Cartridge was created.
 
In addition, the following changes were made:
 
 - Section 11.2 Exclusion criteria, criterion 2 was updated (changes in strikethrough and additions in bold): “With the exception of unfractionated heparin during HD, Econcomitant or prior use of anticoagulant/antiplatelet agents (e.g., low molecular weight heparins, warfarin, apixaban, bivalirudin, ticagrelor, edoxaban, dabigatran, rivaroxaban, clopidogrel, prasugrel, ticlopidine, eptifibatide, tirofiban, dipyridamole, diclofenac, and all other NSAIDs) that may affect hemostasis for 2 weeks prior to check-in on Day -8 and throughout the study.” - Section 11.2 Exclusion criteria, criterion 3 was updated (changes in strikethrough and additions in bold): “Use of unfractionated heparin for HD sessions from check-in on Day -8 and throughout the study.” - Section 11.2 Exclusion criteria, criterion 9: The value for hemoglobin concentration at screening was increased from 8.5 g/dL to 10 g/dL. The hemoglobin limit was increased to allow for the possibility of blood loss of up to 228 mL if there is a clot in the dialyzer circuit. Also, the 5 other clinical laboratory values had no specific timing on when these values were required; thus, “at screening” was added for these clinical laboratory tests. - Section 13.6 Dialysate Analysis; this section was added as samples of the dialysate will be taken for future analysis (e.g., assessment of urea or drug level in the dialysate). Samples will be stored for up to 5 years). |

| | |
|----------------------------------|---|

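### Exclusion 9 states the aPTT limit in the opposite direction from its neighbours and does not make clear whether the laboratory limits, including hemoglobin, apply to patients without a bleeding condition

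*Protocol*

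**What the plan says.** Protocol Section 11.2 opens with "Patients must not be enrolled in the study if they meet any of the following criteria", so meeting any one numbered criterion bars enrolment.

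The stem of criterion 9 is "Currently have established underlying inherited or acquired symptomatic bleeding disorders and/or are at risk for excessive bleeding per PI judgment or current active bleeding". After an exception for minor puncture-site bleeding, it passes to six laboratory bullets through the words "which would be expected to occur during the dialysis procedure, with the following values". Among the bullets are:

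- the one on aPTT: "aPTT up to 1.2 x ULN (if >1.2x ULN up to < 1.5 x ULN, with permission of PI and medical monitor) at screening"
- for comparison, the one on INR: "INR > 1.4 at screening"
- the one on hemoglobin: "Hemoglobin concentration < 10 g/dL at screening"

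The other three cover platelets, ALT/AST and total bilirubin. Nothing states whether one bullet or all of them must be met.

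Protocol Section 1 gives the reason for the present hemoglobin figure: "The hemoglobin limit was increased to allow for the possibility of blood loss of up to 228 mL". Sections 8.5 and 13.3 repeat the risk of losing about 228 mL if the dialysis circuit clots.

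**The concern.** An exclusion list should state values that keep a patient out. The aPTT bullet appears to state values that let a patient in, so following it as printed gives the wrong result. The sentence that introduces the bullets also appears to limit every laboratory threshold to patients who already have a bleeding problem. Yet the hemoglobin threshold has a stated purpose, a reserve against circuit blood loss, that has nothing to do with a bleeding problem and applies to anyone dialysed without heparin.

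At stake is whether different staff would make the same enrolment decision from the same screening results, and whether the hemoglobin limit does the job for which it was raised. The SAP listing of subject eligibility (Appendix 16.2.5.1) records the criterion not met, so an unclear criterion also makes that record hard to interpret.

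**Working it through.** There is no plan figure to reproduce. The check compares the bullets and then treats the criterion as a logical rule.

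**Step 1. Direction of the bullets (Protocol Section 11.2, criterion 9).**

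| Bullet | Range listed as excluding | Permission band | Position of the band |
|---|---|---|---|
| Platelets (cells/mm³) | below 100,000 | above 75,000 and below 100,000 | inside the listed range |
| INR | above 1.4 | none | – |
| aPTT (x ULN) | up to 1.2 | above 1.2 and below 1.5 | outside the listed range |
| ALT or AST (x ULN) | above 2 | none | – |
| Total bilirubin (x ULN) | above 1.2 | none | – |
| Hemoglobin (g/dL) | below 10 | none | – |

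Five bullets list abnormal values; aPTT alone lists the normal to mildly raised range. A permission band relaxes an exclusion, so it should lie within the excluded range, as it does for platelets. For aPTT the listed range (at or below 1.2) and the band (above 1.2, below 1.5) do not overlap. Permission makes sense only if values up to 1.2 x ULN were meant as acceptable. Values at or above 1.5 x ULN fall in neither range.

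**Step 2. Scope of the bullets.** Criterion 9 was applied to eight illustrative patients under four readings:

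- A: stem and at least one bullet.
- A2: stem and all six bullets.
- B: stem or any one bullet, aPTT as printed.
- C: as B, but with aPTT turned to match its neighbours. This serves only to isolate the effect of direction.

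Unless varied, the assumed values are platelets 200,000, INR 1.0, aPTT 0.9 x ULN, ALT 0.5 x ULN, bilirubin 0.5 x ULN and hemoglobin 11.5 g/dL. Permission to enrol is set aside.

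| Patient | A | A2 | B | C |
|---|---|---|---|---|
| No bleeding condition, values as above | in | in | **out** | in |
| No bleeding condition, hemoglobin 9 | **in** | **in** | out | out |
| No bleeding condition, aPTT 1.3 x ULN | in | in | in | out |
| No bleeding condition, aPTT 1.6 x ULN | in | in | **in** | out |
| No bleeding condition, INR 2 | in | in | out | out |
| Bleeding condition, values as above | out (aPTT bullet only) | in | out | out |
| Bleeding condition, hemoglobin 9 | out | in | out | out |
| Bleeding condition, aPTT 1.6 x ULN | **in** | in | out | out |

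Here out means excluded by criterion 9 and in means not excluded by it.

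- If the limits are conditional (A, A2), hemoglobin of 9 g/dL without a bleeding condition is not caught. The reversed aPTT bullet then affects only patients who meet the stem. Under A it lets through a patient with a bleeding condition and aPTT of 1.6 x ULN.
- If the limits stand alone (B), hemoglobin of 9 g/dL is caught. The aPTT bullet then excludes the ordinary patient and passes 1.3 and 1.6 x ULN.

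No single reading both bars normal aPTT in general and loses the hemoglobin limit.

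**Step 3. What remains if the limits are conditional.** Hemoglobin below 10 g/dL appears nowhere else as an eligibility limit. Exclusions 4, 5 and 17 and inclusion 7 rest on the investigator's judgment and give no hemoglobin or aPTT threshold.

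**Step 4. Criteria 10 and 11.** The heart-rate line is "< 45 and > 110 bpm", which one reading cannot satisfy literally. Both criteria join screening and check-in with and, where criterion 14 and the opening sentence of criterion 6 use or. The natural meaning is clear enough, so this is minor.

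**The case against.** The strongest reply is that the intent can be recovered. The hemoglobin rationale in Section 1 applies to any patient whose circuit clots, and that section discusses the laboratory values without tying them to bleeding. Exclusion 5 deals with other significant laboratory abnormalities, which suggests that the numbered limits exclude in their own right. The aPTT parenthesis shows that values up to 1.2 x ULN were meant to be acceptable, since otherwise a raised aPTT would be easier to enrol than a normal one. Sites may well have applied that intent. Investigator discretion could also exclude an anemic patient or one with aPTT at or above 1.5 x ULN, and Section 13.3 promises closer hemoglobin follow-up.

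Most of this stands as evidence of intent and of partial cover. It does not settle the text. A fixed limit and a discretionary one are different safeguards, follow-up during dialysis is not an entry limit, and nothing printed says what happens at or above 1.5 x ULN.

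A reader might infer more than the documents support:

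- **That the criterion bars every patient with normal aPTT and also leaves anemic patients unprotected.** These effects need incompatible readings, and discretionary cover remains in either case.
- **That the condition is a bleeding disorder only.** The stem also covers investigator-judged bleeding risk and active bleeding.
- **That adding the study's blood sampling to the circuit loss measures the harm.** The stated rationale concerns 228 mL only, and such a sum says nothing about how many patients the wording affects.
- **That the wording would distort the aPTT results.** SAP Section 7.2.1 divides each post-dose value by the patient's own pre-dose average, which limits the effect of a high starting value, and the protocol itself admits values above 1.2 and below 1.5 x ULN with permission.

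**Conclusion.** The point holds in two separate parts. The aPTT bullet is reversed relative to its five neighbours and is silent at or above 1.5 x ULN; this follows from the printed text alone. The scope of all six limits is ambiguous, and on the conditional reading the fixed hemoglobin limit does not apply to patients without a bleeding condition, contrary to its stated purpose. The second part depends on that reading, which the wording permits but does not compel.

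The size is one limit of six reversed and six of six with unclear scope. The number of patients affected cannot be derived, because the documents give no distribution of screening aPTT or hemoglobin. This is an error in an enrolment rule that should be corrected. It does not show that any patient was wrongly enrolled.

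**What to change.** By protocol amendment, the sponsor should reconcile the stem, the connecting phrase and the aPTT bullet with the purpose given for the hemoglobin limit:

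- Make the bleeding condition a criterion of its own, and list the laboratory limits separately so that each one excludes by itself.
- Write the aPTT bullet in the same direction as its neighbours, using the protocol's existing 1.2 and 1.5 x ULN figures, with the permission band placed as it is for platelets.
- Have the sponsor's clinicians confirm every limit and state the outcome for aPTT at or above 1.5 x ULN. No threshold is proposed here.
- As a minor tidy-up, clarify the heart-rate line in criterion 11 and the joining of screening and check-in in criteria 10 and 11.

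The cost is the wording of an amendment and its approval. No procedure, sample or analysis is added.

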11.3 Early Termination of Patients from the Study

Patient participation in this study may be discontinued for any of the following reasons:

1. Occurrence of any medical condition or circumstance that exposes the patient to substantial risk and/or does not allow the patient to adhere to the requirements of the protocol.
2. If the patient clots the hemodialyzer twice they may be discontinued from the study at the discretion of the PI. If the patient fully clots the hemodialyzer, continuation of the patient in the study will be at the PIs discretion.
3. Any SAE, clinically significant AE, severe laboratory abnormality, intercurrent illness, or other medical condition that indicates to the PI that continued participation is not in the best interest of the patient.
4. Patient's decision to withdraw.
5. Requirement of prohibited concomitant medication.
6. Patient failure to comply with protocol requirements or study related procedures.
7. Termination of the study by the Sponsor, FDA, Celerion, CRU, or other regulatory authorities.

The clinical report will include reason(s) for patient withdrawals as well as details relevant to the patient withdrawal.

If a patient is withdrawn from the trial prior to study completion, the patient will undergo all procedures scheduled for early termination as the situation allows (see the Study Events Flow Chart ([Section 6](#))). Any patient withdrawn due to an AE (whether serious or non-serious) or clinically significant abnormal laboratory test values will be evaluated by the PI or a monitoring physician and will be treated and/or followed up until the symptoms or values return to normal or acceptable levels, as judged by the PI or designee.

11.4 Study Restrictions

11.4.1 Prohibitions and Concomitant Medication

Consumption of foods and beverages containing the following substances will be prohibited as indicated:

- Xanthines/caffeine: 48 hours prior to dosing and throughout the period of sample collection (small amounts of caffeine derived from normal foodstuffs e.g., 250 mL/8 oz./1 cup decaffeinated coffee or other decaffeinated beverage, per day, with the exception of espresso; 45 g/1.5 oz. chocolate bar, per day, would not be considered a deviation to this restriction);
- Alcohol: 48 hours prior to dosing and throughout the period of sample collection;

Concomitant medications will be listed, recorded, and allowed except for those listed as prohibited in the exclusion criteria in [Section 11.2](#). It is understood and will be considered that treatment with certain drugs or cessation of treatment with certain drugs (e.g., drugs for hypertension) may have adverse effects and could interfere with the evaluation of the primary outcome measures of the study.

After randomization, acetaminophen (up to 2 g per 24 hours) may be administered, for fever or chronic pain control, at the discretion of the PI or designee. Administration of opioids for certain types of pain management may be allowed.

If deviations occur, the PI or designee in consultation with the Sponsor if needed will decide on a case-by-case basis whether the patient may continue participation in the study.

11.4.2 Meals

At the CRU, meals and/or snacks and fluids will be provided at appropriate times following check-in and throughout the study as per the clinical site standard procedure.

11.4.3 Activity

On Day 1, as dosing will be immediately after the start of the hemodialysis session, patients will be dosed in the same position as required for their hemodialysis session. Patients will maintain that position for the whole hemodialysis session, as per standard HD procedure, except when they are supine or semi-reclined for other study procedures. At other times, there will be no specific activity restrictions. However, should AEs occur at any time, patients may be placed in an appropriate position.

Patients will be instructed to refrain from strenuous exercise which could cause muscle aches or injury, including contact sports at any time from 48 hours prior to check-in on Day -8 and throughout the study.

12 TREATMENTS

12.1 Treatments Administered

A separate dosing manual will detail the drug preparation and treatment administration to be followed for this study.

Xisomab 3G3 and matching placebo will be supplied as sterile powder for injection via the IV route, upon reconstitution.

Investigational materials will be provided by the Sponsor as in [Table 3](#).

Table 3: Identity of Investigational Products

| Product | Description |
|---------|---|
| Test | Lyophilized xisomab 3G3 (~15 mg/mL) sterile powder for injection in formulation buffer (8% sucrose, 10 mM histidine, 30 mM arginine HCl, 10 mM methionine, 80 ppm polysorbate 80, pH 5.4) |
| Placebo | Lyophilized formulation buffer (8% sucrose, 10 mM histidine, 30 mM arginine HCl, 10 mM methionine, 80 ppm polysorbate 80, pH 5.4) |

An unblinded pharmacist will be responsible for providing xisomab 3G3 or placebo to the blinded study personnel for administration via injection into the proximal hemodialysis line as per the randomization scheme.

Patients will be enrolled into Cohort 1 or Cohort 2. Within a cohort, patients will be randomized to active drug or placebo as summarized in [Table 2](#).

Patients will receive a single infusion dose of 0.25 mg/kg xisomab 3G3, 0.5 mg/kg xisomab 3G3, or matching placebo on Day 1 at Hour 0. The dose will be administered proximal to the dialyzer cartridge, into the arterial line immediately after start of HD.

Hour 0 will correspond to the start of the xisomab 3G3 infusion. The time at which the infusion is started and stopped must be recorded.

The patient weight recorded at check-in will be used to calculate the study drug dose.

Should the need arise to change the infusion rate (i.e., due to an AE), changes to the infusion rate and the times at which those changes are made will be documented.

